2. STUDY OBJECTIVES

Primary objective

To determine whether the use of RxConnect as a prescribing aid, when compared with usual practice decreases or increases the number of prescribing errors

Secondary objectives

To determine whether the use of RxConnect as a prescribing aid, when compared with usual practice-

- 1. Decreases or increases the magnitude of dose errors
- 2. Decreases or increases the time to prescribe a medication
- 3. Decreases or increases the mental load as perceived by the prescriber
- 4. Alters the prescribing workflow

To explore the opinions of the participants regarding the use of RxConnect as a prescribing aid and indication-based prescribing more generally.

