The following outcomes will be measured-

Primary outcome measure-

Number of prescribing errors per scenario

• Subcategorised as - Incorrect drug, dose, route, frequency or patient.

Secondary outcome measures-

- The magnitude of any dose errors (deviation from recommended dosing range)
- Time taken to prescribe each medication
- Prescribers perceived mental load per prescribing scenario
- Hierarchical task analysis
- Qualitative feedback from participants

Number and magnitude of prescribing errors

We define a prescribing error as any of the following errors:

- Incorrect prescribed dose: prescribed doses that deviate from the recommended dose in the BNF/ BNFc or local guideline by more than 10%.
 - If the recommended dose is a range, deviations will be calculated from the max/min
 of the range, whichever is closest to the user calculated dose. If there are multiple
 recommended dose options e.g., from the BNF and from local guidelines, the
 researcher will calculate deviations based on the most appropriate source for the
 indication. When all sources are deemed equally valid, the researcher will record
 the smallest deviation allowed.
 - Magnitude of dosing error will be calculated as a percentage deviation from the recommended dose.
- Incorrect prescribed route: a medication prescribed via a route that deviates from the recommended route for the medication and dose as per the BNF/BNFc or local guidelines.
- Incorrect prescribed frequency: a medication prescribed for a frequency that deviates from the recommended frequency or that accumulated to a total daily dose for the medication and dose as per the BNF/BNFc or local guidelines.
- Incorrect patient: a medication order issued to incorrect patient's electronic medication chart.

Time

The length of time for each prescribing scenario will be calculated from the time the participant begins to read the first scenario, and for subsequent scenarios from the time they complete one scenario and move onto the next.

Task load index

At the end of each scenario the user will be provided with an online NASA TLX (task load index) form to complete (8).

Hierarchical task analysis

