Hierarchical task analysis (HTA) will be conducted for each of scenario, a framework will be created apriori based on the anticipated task steps and previous research (9,10), however any additional steps will be added if observed during video analysis. HTA results for participants using RxConnect will be compared to their usual practise.

Qualitative interviews

Following completion of the user testing scenarios, the participant will be invited to take part in a short semi-structured interview regarding their experience of using RxConnect and other more generic questions regarding the use of digital dosing support and indication-based prescribing. (See Appendix 1 for a sample interview guide).

Statistics and data analysis

Sample size

A sample size of 30-50 participants is desirable for this descriptive exploratory mixed methods study. A sample size calculation is therefore not relevant for this study.

Statistical analysis

Categorical data (error counts) from the control arm and intervention arm will be compared using the chi-square test.

Continuous data (magnitude of error, time, task load) will be measured using Mann-Whitney test for non-parametric data.

Sub analysis will explore the effect of possible confounders will be measured using multivariate logistic regression, subject to effect size and sample size limitations.

Variables which may be accounted for include - group number, scenario number, prescribing scenario complexity, prescriber grade, prescriber speciality, control arm or intervention arm.

Hierarchical task analysis

Hierarchical task analysis will be conducted to provide an overview of the prescribing workflow for the control arm and intervention. Vulnerable process steps can be highlighted if they are associated with increased error or time taken when prescribing the scenarios, along with any feedback from participants during practice, observation or in the qualitative interview.

Thematic analysis

Thematic analysis will be conducted using data from throughout the observations and the qualitative interviews (11).

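### On its plain wording, dose-error magnitude is compared only among orders that contain a dose error, a subset the arm itself shapes, so the test can mislead in either direction

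*Combined protocol and SAP*

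**What the plan says.** Section 2 sets the first secondary objective: whether RxConnect "Decreases or increases the magnitude of dose errors".

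Section 3, Study outcome measures, turns this into the outcome "The magnitude of any dose errors (deviation from recommended dosing range"). Under Number and magnitude of prescribing errors, an incorrect dose covers "prescribed doses that deviate from the recommended dose in the BNF/ BNFc or local guideline by more than 10" per cent, and "Magnitude of dosing error will be calculated as a percentage deviation from the recommended dose". For ranges, "If the recommended dose is a range, deviations will be calculated from the max/min" of the range, whichever end is nearer.

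Section 3, Statistical analysis, states "Continuous data (magnitude of error, time, task load) will be measured using Mann-Whitney test for non-parametric data". The only adjusted analysis is the one in which "Sub analysis will explore the effect of possible confounders will be measured using multivariate logistic regression".

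No section gives a value for an order without a dose error, names the set of orders that enters the magnitude test, or says how that test is to be read with the error count.

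**The concern.** Random allocation to Group 1 or Group 2 makes the two arms comparable over all orders. It does not make the erroneous orders in one arm comparable with those in the other, because RxConnect may change which orders become erroneous. A test restricted to errors conditions on something that happens after the arm is applied, and that is also the dose component of the primary outcome. The logistic sub-analysis does not model magnitude and so does not repair this.

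At stake is the answer to the first secondary objective. A tool that prevents many small errors and leaves a few large ones would show a higher typical magnitude among the errors that remain. That could be reported as an increase in dose-error size even though fewer orders went wrong. Other patterns of benefit would be hidden or favoured instead.

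**Working it through.** **Inputs from the plan.** The target is 30-50 participants. The upper end reproduces as 5 per day × 10 days = 50; it is a feasibility count, with no power, alpha or effect size behind it. Table 1 gives 3 test scenarios per arm, so 3 × 30 = 90 to 3 × 50 = 150 orders per arm. The draft procedure in Appendix 2 has 4 scenarios, which would give 60-100 orders per arm if 4 is the total, or 120-200 if it is per arm. Table 1 is used here.

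**Assumptions.** Every error rate and size below is assumed, because the documents give none. Orders are treated as independent, so clustering by participant is ignored. For simplicity, every order without a dose error is set to 0 in the all-orders analysis.

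**Count example, 150 orders per arm.** Control has 20 errors of 20% and 10 of 100%. RxConnect has 4 of 20% and 10 of 100%. RxConnect has fewer small errors and the same number of large ones.

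- Errors only, means: control (20 × 20 + 10 × 100)/30 = 46.7%; RxConnect (4 × 20 + 10 × 100)/14 = 77.1%. The medians are 20% and 100%.
- Errors only, rank comparison: of 14 × 30 = 420 pairs, RxConnect is larger in 10 × 20 = 200 and tied in 4 × 20 + 10 × 10 = 180. So P(RxConnect larger), counting ties as half, is (200 + 90)/420 = 0.69; p = 0.020, against RxConnect.
- All orders, means: 1,400/150 = 9.3% and 1,080/150 = 7.2%.
- All orders, rank comparison: P(RxConnect larger) = 0.45; p = 0.015, in favour of RxConnect.

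The same data give opposite significant answers, depending on an analysis set that the plan does not name.

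**Simulation, 90 and 150 orders per arm.** Control has 15% small errors (11-50% off) and 5% large (100-900% off). Two-sided Mann-Whitney at 5%.

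- *Only small errors removed (15% to 3%; large stay at 5%).* About 90 × 0.08 = 7 to 150 × 0.08 = 12 RxConnect orders enter the errors-only test. It is significant against RxConnect in 28% (90 orders) and 47% (150). The all-orders rank test is significant in its favour in 61% and 83%. Taking mid-points of 30.5% and 500%, expected deviation per order is 0.15 × 30.5 + 0.05 × 500 = 29.6% for control and 0.03 × 30.5 + 0.05 × 500 = 25.9% for RxConnect.
- *Better on both (80% of small and 30% of large errors removed).* The errors-only test is still significant against RxConnect in 17-26%.
- *Both kinds halved.* The errors-only test is significant against RxConnect in about 2%. It sees no difference, although half the errors have gone.
- *Mainly large errors removed (5% to 1%; small 15% to 10%).* The errors-only test is significant in RxConnect's favour in 8-11% and against it in under 0.5%.

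These percentages move by a few points between simulation runs. A second error distribution (10% plus a lognormal, median 40%, log-SD 1; small means 50% or less; control error rates 10-30%) gave the same pattern. With 80% of small errors and no large ones removed, the errors-only test was significant against RxConnect in 13-65% of runs.

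**The case against.** **The analysis set is inferred.** The plan never says that orders without an error are left out, and the parenthesis in the outcome line could be applied to every order, with 0 inside the range. This stands. A reader might infer that the plan has committed itself to an errors-only test; the documents support only that this is the plain reading. Both readings call for the same added sentence.

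**The reversal depends on the example.** This also stands. A reader might infer that the planned test will make RxConnect look worse. The documents give no rates to support that, and the bias can vanish or run the other way. Even in the adverse example, the all-orders mean is higher with RxConnect in about 40% of simulated trials, because a few large errors dominate it.

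**An all-orders test answers a different question.** With 0 for 80-92% of orders, a rank test largely repeats the error-count comparison. When both kinds of error are halved and their size distribution is unchanged, it is significant for RxConnect in 48-66% of runs. This is a real cost and shapes the fix.

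**Error counts are primary and the study is exploratory.** A fall in errors would be reported beside the magnitude result, which limits the harm to a careful reader. It does not make the magnitude test a fair comparison, and nothing in the plan links the two results.

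**The range rule.** A reader might infer that a mid-range dose would be scored as an error, because deviation is measured from the nearer end. That is strained: the rule applies where the range is itself the recommended dose, so a dose inside it does not deviate, and the outcome line speaks of deviation from the range.

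**Conclusion.** The concern holds in a limited form. As worded, dose-error magnitude has a value only for orders already classed as dose errors, and a between-arm test on those values is not protected by the randomised arm order. That follows from the definitions and needs no assumed rates.

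The direction and size do need assumptions. At the plan's own 90-150 orders per arm, the errors-only test can be significantly against a tool that removes only small errors (28-47% of runs), nearly blind to one that halves both kinds (about 2% against), or significantly favourable to one that mainly removes large errors (8-11%). These figures rest on assumed error rates and sizes and on independent orders. They show what the test can do and do not predict what this study will find.

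**What to change.** Change the outcome and analysis text of section 3 as follows.

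1. Define percentage deviation for every completed order, with 0 for a dose inside the recommended range or equal to the recommended dose. One clause confirming that an in-range dose has zero deviation settles the range rule.
2. Compare deviation between arms over all completed orders with a method that respects participant and scenario. Show the mean difference and the share of orders above fixed, pre-stated deviation cut-offs, and do not rely on a rank test alone.
3. Show magnitude among erroneous orders descriptively, without a test, next to the error counts in each arm.
4. State that the all-orders comparison combines how often errors occur with how large they are, so it must not be reported as a change in error size alone.

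The cost is a few sentences and no new data. The downsides are many zeros, so medians may be 0, and a mean that is sensitive to a few large errors. The number of test scenarios in Table 1 and Appendix 2 should be reconciled at the same time, since it sets the number of orders per arm.

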4. PARTICIPANT RECRUITMENT

A convenience sample of study participants will be recruited from across Imperial College NHS Healthcare Trust. Study participants will be doctors and non-medical prescribers whose usual course of work involves the prescribing of medication.

Targeted sampling may be conducted to gain participants from a wide range of specialities/ levels of seniority including but not limited to-

- Seniority-
 - Foundation Year 1 and 2, Senior House Officers, Registrars, Consultants, Non-medical prescribers (nurses and pharmacists)
 - Specialities,
 - Medical, Surgical, Paediatrics, Neonatal, Emergency medicine

Department leads and managers will be approached to gain permission prior to any approach of relevant medical staff and will be asked to disseminate invitations to participate in this study. Staff will be sent an email via their trust email address via the departments 'email group'. In addition, an advert will be placed on the trust intranet and further advertisement of the study through word of mouth via established working relationships within ICHT and ICL.

Participants will be provided with a participant information sheet at least a week prior to commencing any recruitment/data collection.

On the day of participating, participants will have the option to ask any further questions before deciding to take part and a copy of the participant information sheet will be available as either paper copy or via email as a PDF.

As participants will be NHS staff, there will be an expectation that participants will have adequate English language skills (reading, written and verbal) to be able to provide informed consent and participate. However, if adaptations are required for a member of staff to participate, (such as information sheets printed in larger font/different colours) this will be accommodated as per any normal adaptations required for working.

Participation in the study should take approximately 90 minutes and will not detract from clinical duties, where possible participation should be during non-clinical hours and/or when appropriate clinical cover is available.

Inclusion Criteria

- Willingness to consent and participate
- Medical doctor Foundation year 1 and above OR registered non-medical prescriber (e.g. nurses or pharmacists)
- Regular (at least weekly) experience in prescribing medications as part of working role

Exclusion Criteria

- Infrequent prescribing practice (less than once a week)
- Not willing to participate

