 - How did this compare with your current prescribing practice?
- What effect do you think a system such as RxConnect could have on your prescribing practice?

- o If positive, in what way?
- o If negative, in what way?
- Is there anything that you think would benefit from changing/improving?

Indication-based prescribing workflow questions -

- Did you utilise the option to search by indication as opposed to by medication first?
- How does this align with your current prescribing workflow, both your mental workflow and decision making as well as the physical act of prescribing, for example entering the information onto the prescription?
- Would you consider an indication-*first* prescribing workflow to be better/worse/the same as current prescribing workflows. For example, searching for an indication and then selecting a medication, rather than searching for the medication.

Probes -

- Can you expand on that
- Do you have any examples
 - where this would have been useful...?
 - where this may have hindered...?
 - specific patient groups
 - specific medication types antimicrobial stewardship

10. Appendix 2: Draft Study session standard operating procedure

- 1. Participant will have already received an invitation to participate and agreed a time to take part in the study.
- 2. Participant arrives at pre-specified time, confirms they have received the PIS and has had any questions answered.

- 3. Participant to complete the consent form and an online copy to be sent to the participant to retain for their own records. Participants will be asked to remove or cover any name badges that may identify themselves.
- 4. Audio-visual recording to begin.
- 5. Participant training and briefing-

Participant RxConnect training-

A brief introductory video to be played to the participant showing how to use RxConnect.

Participant study briefing-

Participants to be briefed as to the purpose of the user testing and that scenarios will be presented that may cover a number of conditions, complexities and potentially error prone prescribing tasks, e.g. patients with contraindicated conditions, considerations and less frequently prescribed medications.

- 6. Participant encouraged to 'think aloud' when completing the following tasks. Participants are provided with two prescribing practice scenarios to complete using RxConnect and document the medication order on the paper form provided.

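### An omitted order or abandoned scenario meets none of the error definitions, and the plan has no rule or denominator for non-completion

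*Combined protocol and SAP*

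**What the plan says.** Section 3 (Study outcome measures) gives the primary outcome as "Number of prescribing errors per scenario", followed by "Subcategorised as - Incorrect drug, dose, route, frequency or patient". Under Number and magnitude of prescribing errors, the definition opens with "We define a prescribing error as any of the following errors" and has four items:

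- **Dose:** a prescribed dose more than 10% away from the recommendation.
- **Route:** "a medication prescribed via a route that deviates from the recommended route".
- **Frequency:** "a medication prescribed for a frequency that deviates from the recommended frequency", or a related problem with the total daily dose.
- **Patient:** an order issued on the wrong patient's chart.

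The wrong-drug subcategory has no definition of its own.

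Statistical analysis compares error counts between arms by chi-square. It states no denominator and no handling of unfinished scenarios. Withdrawal Criteria (Section 4) covers withdrawn consent only. The timing rule runs from one completed scenario to the next and does not mention a scenario that is not completed. Appendix 2, step 5, says the tasks may include "potentially error prone prescribing tasks, e.g. patients with contraindicated conditions, considerations and less frequently prescribed medications".

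**The concern.** Failing to produce an order is one way in which a prescribing aid can fail. A participant might get no usable recommendation from the prototype interface, give up searching several resources in the control arm, or leave out a drug that the scenario requires. None of these meets a listed error, although each is a failure of the task.

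The routes to a missing order differ by arm. With RxConnect, the prototype auto-populates an order form. In control, the participant looks up the information and enters the order in Cerner. Non-completion could therefore differ between arms, and the primary comparison would then depend on a scoring choice that the plan does not make. Because the study is descriptive, readers will look mainly at the direction of the difference, which that choice can affect.

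**Working it through.** **1. What triggers each error.** Dose needs a prescribed dose. Route and frequency need a prescribed medication. Patient needs an issued order. Wrong drug, though undefined, presupposes a chosen drug. A scenario with no order triggers none of the five, so its literal count is zero.

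**2. Whether another section repairs this.** Statistical analysis has no non-completion rule, and Withdrawal Criteria concerns consent. Appendix 2 tells participants to complete the scenarios but does not say what happens if they do not. Hierarchical task analysis and video could show an abandoned task, but neither feeds the error count.

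**3. Inputs for an illustration.** The plan states no error or non-completion rate, so there is no figure of its own to reproduce. From the documents: 30-50 participants and three test scenarios per arm (Table 1), hence 30 × 3 = 90 to 50 × 3 = 150 attempts per arm. Assumed: one required order and at most one error per scenario; error rate e per written order of 10-40%, equal in both arms; non-completion f of 0% in one arm and 10% in the other.

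**4. Formulas.** The observed rate in an arm is:

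- unfinished scored as zero: (1 − f)e
- unfinished excluded: e
- unfinished counted as a failure: f + (1 − f)e

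**5. Results (completing arm vs failing arm).**

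| e | Scored zero | Excluded | Counted as failure |
|---|---|---|---|
| 10% | 10% vs 9% (−1 point) | 10% vs 10% | 10% vs 19% (+9) |
| 20% | 20% vs 18% (−2) | 20% vs 20% | 20% vs 28% (+8) |
| 30% | 30% vs 27% (−3) | 30% vs 30% | 30% vs 37% (+7) |
| 40% | 40% vs 36% (−4) | 40% vs 40% | 40% vs 46% (+6) |

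Zero-scoring makes the failing arm look 1-4 points better. Counting failures shows it 6-9 points worse.

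**6. When exclusion is not neutral.** The table makes exclusion harmless because unfinished scenarios are assumed to be no harder than the rest. Take the opposite extreme: 30% of scenarios would have been wrong, and the unfinished ones are all among them. Exclusion then gives (0.30 − f)/(1 − f):

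- f = 5%: 0.25/0.95 = 26.3%
- f = 10%: 0.20/0.90 = 22.2%
- f = 15%: 0.15/0.85 = 17.6%

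Zero-scoring gives 25%, 20% and 15%. Exclusion recovers only a small part of the 30%.

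**The case against.** The strongest reply is that the documents are silent and do not state a rule. They never say that an unfinished scenario scores zero, and exclusion is equally open to the analyst. This stands. What can be said is that the literal definition adds no error and that the handling is unspecified. Silence does not settle the matter, however, because exclusion is neutral only under the assumption in step 5 of the working.

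Second, the documents do not show that non-completion will happen. There is a training video, two practice tasks with an optional third, a researcher in the room, and full access to usual resources in control. Participants prescribe at least weekly. A reader might infer from "Participation in the study should take approximately 90 minutes" that people will run out of time, but that is an approximate duration and not a cut-off. The workload is also unclear, since Table 1 lists six test scenarios and Appendix 2, step 8, says four. The argument therefore rests on failure related to the tool or to task difficulty, not on the clock.

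Third, the effect of zero-scoring is small against sampling noise. Around a 30% rate, the standard error of a difference is √(2 × 0.30 × 0.70/n): 6.8 points with 90 attempts per arm and 5.3 points with 150, ignoring clustering. This also stands, but a systematic shift does not shrink with more participants.

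Fourth, counting an abandoned task as a prescribing error mixes a usability failure with wrong prescribing. That is a fair criticism of a single merged count, and a reason to report omissions separately.

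Finally, a reader might infer from the mention of contraindicated conditions that withholding is the correct answer in some scenarios. The scenarios are not in the documents, and such a case might equally call for a different drug. It follows only that a blanket rule that no order is an error could be wrong.

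**Conclusion.** The gap is real, and its size is unknown. Every error category needs a written order, and nothing elsewhere in the plan says how omitted orders or unfinished scenarios enter the primary comparison. If non-completion differs by arm, zero-scoring favours the arm that fails more often, and exclusion does so when the harder tasks are left unfinished. The effect is nil if all scenarios are completed. The ranges of 1-4 and 6-9 points rest wholly on the assumed rates.

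A reader might go further and infer that the plan's result will have the wrong sign, or that it will flatter RxConnect. The documents support neither. They do not indicate which arm would fail more often, and the change of direction in the illustration depends on the assumed rates and on counting each omission as one error. The point should be settled before data collection, but it does not invalidate an exploratory design.

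**What to change.** Before data collection:

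1. For each scenario, mark the required order or orders and the accepted end states, including any where no order is accepted.
2. Add to the definition in Section 3: *Omission: an order required by the scenario is not completed.* Count one error per missing order, identically in both arms.
3. Report omissions as their own subcategory beside drug, dose, route, frequency and patient. Show the primary comparison with and without them, using all attempted scenarios as the denominator.
4. Reconcile the number of test scenarios in Table 1 and Appendix 2, since the denominator depends on it.
5. Flag the time of any unfinished scenario as incomplete.

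The cost is one line in the definition, one column on the scoring sheet and a short key for each scenario, with no extra burden on participants. The downside is small: error counts rise slightly, and a usability failure is counted with prescribing errors. Separate reporting makes that visible and keeps the count without omissions available.
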